### Description of the Intervention

We will randomize patients, using computer-generated random numbers, to one of two treatment arms:

- a) an FDA-authorized prescription digital CBT-I therapeutic treatment
- or
- b) an interactive, attention-matched, internet-based placebo control program.

At the beginning of the intervention, study staff will give instructions on the use of the programs via zoom.

Throughout the intervention, study staff will call the participants weekly to give further clarifications and answer questions. Somryst is a 9-week program that delivers digital CBT-I therapeutic content, and can be used on a mobile device, such as a smartphone or tablet. CBT-I is a neurobehavioral treatment which focuses on addressing the maladaptive behaviors, routines, and dysfunctional thoughts that perpetuate sleep problems, regardless of the cause of sleep problems. CBT-I can be conceptualized as six sessions or cores that deliver proven behavioral and cognitive treatment strategies.

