## Study Schedule & Procedure Summary

### SCHEDULE OF EVALUATIONS

ASSESSMENT	Recruitment Pre-screening & Consent	Screening/ Assessment	Baseline Measures/ Start of Trial	9 Weeks/ End of Trial Follow-up
Inclusion/Exclusion Criteria	X			
Medical History	X	X		
Insomnia Severity Index	X	X		X
Pittsburg Sleep Quality Index		X		X
SF-36			X	X
Epworth Sleepiness Scale			X	X
Quality of Life			X	X
Cognitive function			X	X
Geriatric Depression Scale			X	
24-h Actigraphy (3 days)			X	X
Cognitive Assessment Battery			X	X

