## B. FOLLOW-UP MEASURES

Once intervention is completed,

- Feedback at the end of trial via survey and phone follow-up (if needed)
- Follow-up (3-day actigraphy & questionnaires + Cognitive Assessments)
- Follow-up at 24 weeks:
- Final follow-up actigraphy watch measurement
- Follow-up of cognitive assessment + questionnaires

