3 Follow-up and outcome measures. The primary goal of this research is to pilot test the feasibility of implementing this CBT-I program in patients with MCI or mild AD. Following the last session of CBT-I, participants will be asked to report their satisfaction and acceptability of the treatment. We will also assess eligibility, consent, and retention rates, as well as data quality and completeness. To explore the initial effects of this treatment on sleep and cognition, we will repeat baseline measurements, including the neuropsychological battery and the questionnaires (ISI, PSQI, ESS and SF-36) towards the end of the intervention.

STATISTICAL ANALYSES

To assess the randomization, baseline demographic and clinical characteristics will be compared between arms using parametric (e.g. t-test) or nonparametric test (e.g. chi-square, Wilcoxon tests); variables that are not balanced across treatment arms will be adjusted for in subsequent analyses. The primary analysis will use the intent-to-treat principle. Secondary subgroup analyses will assess the role of treatment adherence on outcomes, using measures of compliance applicable to both study arms, thus avoiding the well-known biases of a “compliers only” analysis.

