For Aim 2 and the Exploratory Aim, we will use t-tests, Wilcoxon or chi-square tests to compare between the treatment and non-treatment groups the change scores in: 1) circadian rhythms parameters (e.g. amplitude, and overall rhythmicity); 2) frequency and length of day naps; 3) quality of nocturnal sleep (e.g. change in ISI scores; increased sleep duration and efficiency; decreased sleep onset time); 4) reported quality of life (SF-36 scores); 5) cognitive scores. Standardized measures of cognitive performance (z-scores) will be calculated for each participant for each neuropsychological test in the battery. Repeated measures models will be used to examine longitudinal treatment effects. These models will include subject-specific (i.e. intercept term) and fixed effects (treatment group, time and the time*treatment interaction). A significant time*treatment interaction will indicate that changes in outcome measures over time are different in the treatment arms. In order to explore the impact of involvement of caregivers, we will repeat the above analysis between the treatment group with and without involvement of the caregiver. The resulting estimates will be imprecise, and thus useful for trial planning only in combination with external data, expert opinion, and established norms for clinically meaningful effects.

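### The Aim 2 and exploratory change-score tests use only participants with the later value; the SAP gives no missing-data rule and does not say whether these tests or the repeated measures model lead

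*SAP*

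**What the plan says.** The SAP's Statistical Analyses section contains three relevant statements.

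- On principle: "The primary analysis will use the intent-to-treat principle". It defines no analysis set and gives no imputation rule or missing-data assumption.
- On the simple comparisons, which serve Aim 2 and the exploratory outcomes: "we will use t-tests, Wilcoxon or chi-square tests to compare between the treatment and non-treatment groups the change scores in" five outcome groups (circadian rhythm, naps, nocturnal sleep including ISI, SF-36 and cognition).
- In the same paragraph: "Repeated measures models will be used to examine longitudinal treatment effects". On their content: "These models will include subject-specific (i.e. intercept term) and fixed effects (treatment group, time and the time*treatment interaction"). It does not state the estimation method, which visits enter, or whether this model or the simple tests lead.

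On timing, the protocol's Schedule of Evaluations goes from baseline straight to "9 Weeks/ End of Trial Follow-up". The SAP likewise repeats the questionnaires ("ISI, PSQI, ESS and SF-36) towards the end of the intervention"). Between those points, "study staff will call the participants weekly to give further clarifications and answer questions"; no outcome scale is assigned to these calls. Section B of the protocol adds a 24-week visit with actigraphy and "Follow-up of cognitive assessment + questionnaires".

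The protocol's section on withdrawal lets participants stop at any time and does not say whether assessments continue afterwards. Missing data appear under Feasibility as something to be counted, not as something the analysis handles.

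**The concern.** A t-test or Wilcoxon test on change scores silently excludes anyone without the later value. With one scheduled assessment at the end of treatment and none before it, a participant who misses week 9 contributes nothing to the week-9 comparison, although the baseline is known. The result is a completer analysis.

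This matters if the arms lose different kinds of people. Only the active program is described as including sleep restriction, so differential loss is plausible, though no passage predicts it. Change from baseline is correlated with baseline through regression to the mean, so losing severe cases from one arm shifts that arm's mean change even when the treatment effect is the same for everyone.

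The SAP also names two analyses that can give different answers and leaves open which one is reported as the result. The estimates are intended to inform the planning of a later trial. Required sample size varies with 1/effect², so an estimate of -3.32 against a true -4 inflates it by (4/3.32)² = 1.45, and an estimate of -4.68 shrinks it by (4/4.68)² = 0.73.

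**Working it through.** **No figure to reproduce.** The documents give a total of 40 participants and no allocation ratio, alpha, effect size, SD or dropout rate. Everything below is illustrative.

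**Assumed inputs.** ISI SD 4.5 at both visits; true difference in change -4; correlation r between baseline and week 9 of 0.4 to 0.6; control dropout 10% at random; active dropout 30%.

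**Dropout related to baseline severity.** Let z be the standardised baseline, and let the active-arm dropout probability be 1/(1+exp(-(a+bz))). Take b = +1 (severe cases leave) or b = -1 (mild cases leave), with a = -1.018 so that dropout is 30% overall. Numerical integration gives a mean z among those who stay of -0.253 for b = +1 and +0.253 for b = -1. Given z, mean change shifts by -(1-r) × SD × z, so the change-score contrast is

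-4 - (1-r) × 4.5 × E[z | stay].

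| Who leaves the active arm | r | Calculation | Change-score result | Error |
|---|---|---|---|---|
| Severe | 0.4 | -4 + 0.6 × 4.5 × 0.253 | -3.32 | 17% too small |
| Severe | 0.6 | -4 + 0.4 × 4.5 × 0.253 | -3.54 | 11% too small |
| Mild | 0.4 | -4 - 0.6 × 4.5 × 0.253 | -4.68 | 17% too large |
| Mild | 0.6 | -4 - 0.4 × 4.5 × 0.253 | -4.46 | 11% too large |

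Large simulations of the same set-up agree to within 0.02 points (range -3.30 to -4.70, so 18% at the extreme). A likelihood analysis that keeps baseline-only participants gives about -4.0 in all four rows. If dropout is random, E[z | stay] = 0 and both methods give -4.

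**Dropout related to poor response.** Keep the same rates and slope, but let active-arm dropout depend on the standardised change, with poor responders leaving. The SD of change is 4.5 × √(2(1-r)), which is 4.93 at r = 0.4 and 4.02 at r = 0.6.

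- Change score: -4 - 4.93 × 0.253 = -5.25, and -4 - 4.02 × 0.253 = -5.02.
- Likelihood analysis (simulated): about -4.9 and -4.8.

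Most of this bias remains, because the week-9 values that drive the dropout are not observed.

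**Size against the noise.** Assume 1:1 allocation. Of 20 per arm, 14 active and 18 control participants remain. The standard error is SD of change × √(1/14 + 1/18), which is 1.76 at r = 0.4 and 1.43 at r = 0.6. With t(30) = 2.04, the 95% half-width is 3.6 or 2.9 points. The baseline-related bias is 0.68/1.76 = 0.39 or 0.46/1.43 = 0.32 of a standard error.

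**At this trial's size.** In 400 simulated trials with 20 per arm and r = 0.5, severe cases leaving the active arm, the change-score mean was -3.37 and the random-intercept model mean was -3.95. The SDs across trials were 1.65 and 1.64, so the model removed nearly all the bias with no loss of precision.

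**The case against.** The case against has real force on several points.

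- **The remedy is mostly planned already.** The repeated measures model, fitted by likelihood, can keep participants who have only a baseline value, or a week-24 value without week 9. What is missing is its rank, the visits it uses and the missing-data assumption.
- **The promise of intent-to-treat is for the primary analysis.** The stated primary goal and primary outcomes are feasibility and acceptability. A reader might infer a flat contradiction of intent-to-treat. The documents do not go that far, because the change-score tests belong to Aim 2 and the Exploratory Aim.
- **A reader might infer that everyone who stops early is lost.** The text does not say so. Someone who stops the program is excluded only if the week-9 assessment is also missed, and a 24-week follow-up is scheduled.
- **A reader might infer that nothing is recorded before week 9.** Somryst includes a daily sleep diary, and the telephone script mentions a diary to all prospective participants. However, the placebo program is not said to include one, the SAP does not name the diary among its compared outcomes, and it cannot supply a missing ISI, SF-36 or cognitive score.
- **The bias is small beside the noise.** It is under half a standard error, under an assumed 20-point imbalance in dropout. The SAP itself warns that the estimates will be imprecise and usable for planning only alongside external data.

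These points limit the scope and weight of the concern. They leave standing that the tests exclude people without the later value, with no missing-data rule and no stated lead analysis.

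**Conclusion.** The concern holds in limited form. The week-9 change-score tests are completer analyses, and nothing in the SAP makes the better of its two planned methods the leading one. Under the assumed 30%/10% dropout related to baseline severity, the error is about 11% to 17% of a 4-point ISI effect, towards or away from zero according to who leaves. It is zero if dropout is random. SD, effect, correlation and dropout rates are all assumptions.

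It would be wrong to conclude that the likelihood model cures the problem in general. It does so for dropout explained by observed values. When poor responders leave, it still gives about -4.8 to -4.9 against a true -4. Nor does the calculation show a need for an extra mid-treatment ISI: two visits are enough to recover the effect when dropout depends on baseline, and an added ISI would do nothing for actigraphy, SF-36 or cognition.

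The feasibility outcomes are unaffected. This is a worthwhile, inexpensive improvement to secondary and exploratory analyses in a 40-person pilot.

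**What to change.** In the SAP's Statistical Analyses section:

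1. Name the repeated measures model as the lead analysis for the week-9 contrast. Fit it by likelihood to all randomised participants with a baseline value, using baseline, week 9 and week 24 data, with time entered as visit so that the week-9 difference is estimated directly.
2. Label the t-test, Wilcoxon and chi-square comparisons of change as supportive completer analyses.
3. Report the number of missing week-9 values by arm.
4. Add one simple sensitivity analysis for dropout related to poor response, for example by shifting the assumed week-9 values of active-arm dropouts over a stated range.

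The cost is a few sentences and one short extra analysis, with no new data collection. The downside is that the lead analysis assumes dropout depends only on observed values, which is why item 4 is needed.

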Official title: Napping, Sleep, Cognitive Decline and Risk of Alzheimer's Disease

NCT#: NCT03256539

Document date: 09/21/2023

SleepTIGHT Statistical Analysis Plan

(Sleep Therapeutics Intervention to improve coGnitive HealTh)

***Full Study Title: Napping, Sleep, Cognitive Decline and Risk of
Alzheimer's Disease***

Principal Investigator: [name]

University of California, San Francisco

[name]

[name]

[contact]

Sponsor

National Institutes of Health

STUDY AIMS

The overall objective is to develop a CBT-I program for people with MCI/ mild Alzheimer's disease and sleep disturbances, pilot test its feasibility, and elucidate its preliminary effects on sleep, cognition and quality of life, with the ultimate aim of decreasing risk of Alzheimer's onset or progression.

Aim 1: To develop a CBT-I program and test its feasibility and acceptability in patients with MCI/ mild Alzheimer's disease and sleep disturbances.

Aim 2: To elucidate the effects of the CBT-I program on patients' subjective and objective sleep quality.

Exploratory Aim: To collect pilot data and explore preliminary effects of 1) the CBT-I program on cognition and quality of life and 2) involving caregivers in the program.

PROCEDURES

We plan to study older adults (aged 65 and above) with MCI or mild AD. Patients will be identified from a combination of online sources, including the UCSF CTSI Electronic Health Record services (MyChart), Researchmatch.org and social media postings, as well as the UCSF Memory and Aging Center (MAC, Director: [name], co-founders include [name]). *The attached figure* outlines the study visits and related measurements.

1. Baseline screening/ Randomization

When a potential participant is identified or expresses interest in the study, study staff will contact them to explain study procedures and go through the key points of the consent form. Once consented, study staff will administer clinical interviews via zoom to assess insomnia, medical history, mood and QDRS-derived global CDR to determine eligibility and obtain visual proof of written informed consent. Eligible participants who consent will be scheduled for a baseline assessment via zoom within 2 weeks of enrollment. The measures described above will also serve as part of the baseline measures.

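### The SAP reads any significant time-by-treatment interaction as an arm difference across at least ten outcomes, with no lead outcome or time point for Aim 2

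*SAP*

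**What the plan says.** The SAP's Study Aims give the effect on sleep an aim of its own, apart from the Exploratory Aim: "Aim 2: To elucidate the effects of the CBT-I program on patients' subjective and objective sleep quality".

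For Aim 2 and the Exploratory Aim together, the Statistical Analyses section compares change scores between arms on five groups of outcomes:

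- circadian: "circadian rhythms parameters (e.g. amplitude, and overall rhythmicity"
- naps: "frequency and length of day naps"
- night-time sleep: "quality of nocturnal sleep (e.g. change in ISI scores; increased sleep duration and efficiency; decreased sleep onset time"
- quality of life: "reported quality of life (SF-36 scores", without saying which scores
- cognition: "Standardized measures of cognitive performance (z-scores) will be calculated for each participant for each neuropsychological test in the battery", with the number of tests not given.

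Repeated measures models follow, with this rule: "A significant time*treatment interaction will indicate that changes in outcome measures over time are different in the treatment arms".

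Neither document states an alpha, a lead efficacy outcome, an analysis time point or an approach to multiple outcomes. The Protocol's Follow-up Measures section adds a 24-week assessment to the one at the end of treatment.

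Two statements limit how far the results may be taken. The SAP's follow-up section makes feasibility the primary goal, and the Protocol's primary outcomes are feasibility and acceptability. The SAP also closes by calling the resulting estimates imprecise and of use for planning a trial only when combined with outside data, expert judgement and accepted norms for a meaningful effect.

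**The concern.** A rule that reads significance as a difference between arms is harmless for one outcome fixed in advance. Applied to an open list with no lead outcome, it lets the data choose which result represents Aim 2. Two things follow. The chance that something crosses the threshold when nothing is going on rises well above the nominal level. In addition, a small trial reaches significance only when the observed difference is large, so an effect picked out because it was significant tends to be too big.

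What is at stake is planning. If the next trial's outcome and effect size are taken from whichever result was significant here, that trial may have the wrong endpoint or too few patients. The closing caveat in the SAP deals with imprecision. It does not say which outcome will be carried forward, so it does not deal with selection.

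**Working it through.** The plan gives no alpha, power, effect size or error rate, so there is no stated figure to reproduce.

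**Inputs**

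- Outcomes, from the SAP list: 2 circadian + 2 nap + 4 night-time sleep (ISI, duration, efficiency, onset time) + at least 1 SF-36 + at least 1 cognitive = at least 10. PSQI and ESS are repeated at the end of the intervention according to the SAP's follow-up section. If they are tested, the count is 12.
- Alpha: not stated. Assumed two-sided 0.05 per outcome, so 0.025 in the direction favouring CBT-I.
- Sample size: 40 (Protocol synopsis). The allocation ratio is not stated. Assumed 1:1, 20 per arm.
- Correlation between outcomes: not stated. Range shown from 0 to 0.7, equal for all pairs.

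**Chance of at least one false positive, no true effect on any outcome**

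Independent outcomes, either direction: 1 − 0.95^k.

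- k = 10: 1 − 0.95^10 = 40.1%
- k = 12: 1 − 0.95^12 = 46.0%

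Independent outcomes, favouring CBT-I only: 1 − 0.975^k.

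- k = 10: 22.4%
- k = 12: 26.2%

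Correlated outcomes, by simulation of 200,000 sets of equicorrelated normal test statistics:

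| Outcomes | Correlation | Either direction | Favouring CBT-I |
|---|---|---|---|
| 10 | 0.3 | 35% | 18% |
| 10 | 0.5 | 29% | 14% |
| 10 | 0.7 | 21% | 11% |
| 12 | 0.3 | 40% | 20% |
| 12 | 0.5 | 32% | 16% |
| 12 | 0.7 | 23% | 12% |

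The range over both counts is 21–46% in either direction and 11–26% favouring CBT-I. These figures count one test per outcome. They leave out the unspecified choice between t-test, Wilcoxon and chi-square, the 24-week visit, and the repeats by adherence and caregiver involvement.

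**Inflation of effects selected by significance**

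With 20 per arm, a two-sample t-test (38 degrees of freedom, critical value 2.024) is significant only if the observed standardised difference exceeds 2.024 × √(2/20) = 0.64.

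In simulation, a true 0.5 SD effect is significant about 34% of the time. The significant estimates then average 0.83 in true SD units, or 0.87 when divided by the sample SD: about 0.85, or roughly 1.7 times the truth (0.85/0.5).

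**The case against.** The strongest reply is that efficacy is not what this trial is for. Feasibility and acceptability are primary, the effects work is described as preliminary, and the SAP says the estimates can inform planning only alongside outside evidence. All of that stands, and it is why the point is modest. The SAP does not set up a confirmatory efficacy claim. Two qualifications remain: Aim 2 is not among the aims labelled exploratory, and the caveat comes straight after the caregiver analysis, so how much it covers is unclear.

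Four stronger readings may occur to a reader, and the documents do not support them.

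- *A false efficacy signal is likely.* For the 10 to 12 outcomes that can be counted, the chance stays below one half, and is at most about 26% in favour of CBT-I. With independent outcomes it takes 14 to pass 50% (1 − 0.95^14 = 51.2%), and the documents do not give such a count. Sleep measures on the same patient are also unlikely to be independent.
- *Most significant results would be chance.* That depends on how many outcomes truly respond, which is unknown. At 35% power (0.5 SD effect, normal approximation), false positives outnumber true ones only if fewer than 0.05/(0.05 + 0.35) = 1 in 8 outcomes is truly affected.
- *Every outcome is tested twice.* With two visits, complete data and a random intercept, the change-score test and the interaction test coincide. They part only with missing data, covariates or the 24-week visit.
- *The interaction sentence is itself wrong.* It is the ordinary reading of the term. The fault is that no lead outcome, time point or alpha surrounds it.

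**Conclusion.** The concern holds as a modest one. The significance rule, applied to at least 10 outcomes on an open list with no lead outcome or time point for Aim 2, carries roughly a 21–46% chance of at least one false-positive result if there is no true effect, and 11–26% for one favouring CBT-I. Small-to-moderate true effects that do reach significance will be overstated, by about two-thirds for a true effect of 0.5 SD. These sizes rest on an assumed two-sided alpha of 0.05, 1:1 allocation and correlations of 0 to 0.7.

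The rule is at odds with the SAP's own statement that its estimates are imprecise and need outside support. Bringing the two into line is worthwhile. It has no bearing on the feasibility objectives.

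**What to change.** Cheap improvement, SAP wording only:

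1. Name one lead outcome and time point for Aim 2. One suitable choice is the between-arm difference in ISI at week 9, adjusted for baseline ISI. ISI is already an eligibility measure, and the Protocol's Schedule of Evaluations collects it before treatment and at week 9. That schedule has two pre-treatment ISI readings, so say which is the baseline. With equal SDs and baseline-to-follow-up correlation r, the adjusted analysis has variance proportional to 1 − r², against 2(1 − r) for the change score. The ratio is (1 + r)/2, for example 0.75 at r = 0.5, so precision improves.
2. Replace the sentence beginning "A significant time*treatment interaction will indicate". Label all other sleep, quality-of-life and cognitive outcomes exploratory, and report them as estimates with 95% CIs and no significance claims. At 20 per arm the half-width is about 1.96 × √(2/20) = 0.62 SD, which shows the imprecision directly.

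No alpha correction is required, and no cognitive composite is needed.

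The cost is that the other outcomes can no longer be claimed as significant. ISI also covers only the subjective half of Aim 2, so the objective sleep measures would be reported as estimates. No visit, measurement or participant is added.
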